#### Word of mouth

Word of mouth is often a successful method for recruiting study participants, especially rural individuals. Faculty and staff from the Division of Epidemiology, Biostatistics, and Preventive Medicine, the Prevention Research Center, and the UNM Comprehensive Cancer Center will be emailed a copy of the study flyer, provided approval from leadership (i.e., Division Chief, Director, Associate Directors or Program Leaders). The email will briefly explain the study, and indicate a \$5 e-merchandise card for Amazon will be provided for anyone referring an individual to the study, regardless of final eligibility (referred individual must contact study staff).

*The second screening for individuals identified by the NMTR or self-referrals includes the following eligibility criteria, which are assessed by the study team:*

- Men and women 60 years and older residing in New Mexico
- Previous diagnosis of cancer, completed primary treatment (surgery, radiation, chemotherapy), and not currently being treated for a recurrence. Individuals on hormone

## PROTOCOL TITLE: Videoconferencing for Remote Assessment of Physical Performance

therapy are eligible, e.g., aromatase inhibitors for breast cancer and antiandrogen therapy for prostate cancer.

- Mild-to-moderate physical functional impairment ( $\geq 2$  functions limited a lot or limited a little on the SF36 Physical Function Subscale); representing individuals most at risk for functional decline and most likely to benefit from a home-based lifestyle activity intervention based on our previous research.
- Able to speak, read, & understand English. (Within the NM Hispanic population, 83% are US born and 94% speak English very well. Additionally, this is just a small pilot study.)
- Participating in less than 120 minutes per week of MVPA (determined using Godin Leisure Time Exercise Questionnaire – low respondent burden).
- Living independently and capable of walking 3 blocks without stopping to rest.
- Availability of a family member or friend to be present (for safety) during remote assessment of performance tests (Note: This criterion is in preparation for an intervention trial that will potentially use this videoconferencing remote assessment method. Information regarding the interactions between the participant, family member, and investigator will be used to refine the protocol to be used in the future intervention trial.)
- No severe impairments or pre-existing medical limitations for engaging in daily LPA (e.g., severe orthopedic conditions, pending hip/knee replacement, chronic vertigo, dementia)
- No severe hearing or vision deficits that would inhibit communication with the research team via videoconferencing and tablet use.
- Willing to use a tablet computer and videoconferencing software to communicate with a study team member during the assessment.
- Enough space (12 to 15 feet by 4 feet) to safely conduct the physical function tests.
- Not at high risk for falls (score below 15 on the Fall Risk Assessment portion of the recruitment/eligibility screener). Individuals who score 15 or above will be asked if they would like more information on Fall Prevention, and if yes, will be mailed a brochure from the CDC STEADI Program (see section 13.0).

### 3.1 Exclusion Criteria

- Adults not able to consent are excluded from participation
- Based on the age criterion (60 years and older), individuals who are not yet adults (infants, children, teenagers) may not participate in this study due to the same age criterion above
- Pregnant women may not participate in this study due to the same age criterion above
- Prisoners may not participate in this study as this is a study of free-living individuals

## 4.0 Study-Wide Number of Subjects

This study will enroll 30 to 52 cancer survivors. We will first enroll 10-12 cancer survivors to test proof-of-concept that participants will be able to follow the testing protocol and use the tablet to communicate with the investigator (Phase 1). After refining the testing protocol and materials based on this proof-of-concept test period, we will enroll 10-20 cancer survivors to evaluate the validity of videoconference vs. face-to-face assessment of physical performance (Phase 2). The reliability phase will enroll 5-10 participants who completed the home visit,

## PROTOCOL TITLE: Videoconferencing for Remote Assessment of Physical Performance

and have consented to repeat the study (no home visit with direct observer; only remote assessor; Phase 3). The remote assessment phase will enroll 5-10 new participants to complete the study (no home visit with direct observer; only remote assessor; Phase 4). In order to achieve this accrual target, we estimate that the NMTR may need to contact 350 or more cancer patients identified in the registry due to the number of eligibility criteria and a conservative estimate of 14% participation rate.

## 5.0 Study-Wide Recruitment Methods

NA - This is not a multi-site study; see recruitment methods in section 22.0.

## 6.0 Multi-Site Research

NA - This is a single-site study.

## 7.0 Study Timeline

The proposed validation study is part of a career development award. As such, the first six months will include training for the PI, e.g., shadowing physicians in the clinic and accompanying them on home visits to gain “hands-on” experience with the study population. The actual timeframe for the validation study is 1.5 years, from development to manuscript submission.

Table 3. Study Timeline: 2018 - 2020	Y1	Y2
Training for the PI		
Development		
Validity / Reliability study (30 participants total)		
Pre-test with 10 participants		
Test with 20 other participants		
Analyze Data / Prepare & submit manuscripts		

## 8.0 Study Endpoints

### 8.1 Primary and secondary study endpoints

8.1.a. Proof-of-concept that participants will be able to follow the testing protocol and use the tablet to communicate with the investigator. We will track technology issues (use of tablet, cellular reception, audio and video quality) as well as non-technology issues (understanding of test instructions, safety issues).

8.1.b Evaluation of the validity and reliability of videoconference vs. face-to-face assessment of physical performance. Both performance tests are timed tests (time in seconds to complete the TUG test; number of stands in 30 seconds). The validity

## PROTOCOL TITLE: Videoconferencing for Remote Assessment of Physical Performance

of the videoconference assessment will be evaluated using the limits of agreement statistic, which is the range within which 95% of differences between measurements obtained by 2 methods will lie. The videoconference assessment will be considered valid if the limits of agreement are within a clinically acceptable limit. This limit will be determined *a priori* through discussions between the PI and her mentoring team after the proof-of-concept portion of the study (first 10 participants). This will provide a better idea of inter-rater differences in timing these tests, under ideal conditions (both investigators directly observing the tests at the same time). The clinically acceptable limit will need to take inter-rater difference into account, i.e., a limit that is at or above the inter-rater difference under ideal conditions. Intraclass Correlation Coefficients (ICC) will be used to examine intra-rater and inter-rater reliability of the videoconference assessment of physical performance. Interpretation of ICC values is as follows: 0.75-1.00 = excellent reliability; 0.60-0.74 = good reliability; 0.40-0.59 = fair reliability; and <0.40 = poor reliability.

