## 2.0 Background

Physical functioning, an important patient-reported outcome (PRO), is a key measure of physical health and well-being in older cancer survivors. Self-reported physical function is typically collected by questionnaire (e.g., SF-36, PROMIS, etc.). Objective measures of physical function (i.e., physical performance) are typically collected in a clinic setting (e.g., Short Physical Performance Battery, Rikli and Jones Senior Fitness Test, etc.). Currently, low-cost, valid, reliable, and easy to use methods to remotely assess physical performance in older adults do not exist. Wearable sensors are very expensive, proprietary, and/or require technicians present for testing.

Telerehabilitation studies have been conducted using videoconferencing to assess physical performance; however, to date, these studies have included a technician or study investigator in the same room as the study participant during the tests. Nor have these studies been tested in rural areas. We propose to evaluate the validity and reliability of using videoconferencing to assess physical performance tests self-administered by older cancer survivors. In order to evaluate validity, a member of the research team will need to be at the participant's home, and in the same room as the participant (face-to-face assessment of performance tests). However, the idea is to test if the participant is able to use the technology (an android tablet with videoconferencing software) to communicate with an off-site research investigator. We will also be testing the feasibility, acceptability, and most importantly the safety of having the participants perform two standard gerontologic physical performance tests in their own home (see below).

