### 8.2 Primary and secondary safety endpoints

All adverse events associated with the performance tests (see section 9.0) will be tracked. The performance tests incorporate movements typically undertaken during normal daily activities (standing from a chair, walking a short distance, sitting on a chair), and thus represent tests that are more likely to be safely performed in the home. For both the proof-of-concept and validation studies, one or more members of the study team will be present in the home during the performance tests. Safety checks will be made prior to the performance tests (see section 13.0 Potential Risks to Subjects / Protection Against Risks).

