## 9.0 Procedures Involved

### *Study Design*

Interested and eligible participants will be scheduled for a home visit (Phases 1 and 2). An android tablet with Wi-Fi and cellular will be used to compare videoconferencing with face-to-face assessment of 2 timed, physical performance tests. The tablet will contain videos demonstrating the performance tests, safety measures, and instructions, with features adapted for older adults (e.g., large font).\*\* Further instructions will be provided by the investigator via videoconferencing. First, we will test proof-of-concept that participants will be able to follow the testing protocol and use the tablet to communicate with the investigator (10-12 participants). While one investigator is in a different room of the house conducting the videoconference assessment, another will be in the same room to directly observe and evaluate the impediments and barriers related to the technology and test protocol. After refining the study protocol and materials, 10-20 participants will be enrolled to evaluate the validity and reliability of videoconference vs. face-to-face assessment of physical performance. The performance tests will be assessed simultaneously by two investigators to eliminate intra-participant variation that would occur with sequential assessments. A simultaneous assessment (face-to-face and remote) vs. sequential assessments avoids learning effects (among high performers) and fatigability (among low performers). One investigator will perform the assessment from a remote location using videoconferencing (provides

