### **13.0 Potential Risks to Subjects / Protection Against Risks**

This validation study poses minimal risk, since a member of the research team will be present during home visits to remotely assess physical performance (Phases 1 and 2). This research team member will be timing the participant as part of the face-to-face assessment to be compared with remote (videoconferencing) assessment. Being in the same room as the participant, this research team member will also be able to supervise the performance tests. For Phases 3 and 4, a friend, neighbor, or family member of the participant must be present during the tests. The two tests were chosen since they incorporate movements typically undertaken during normal daily activities (standing from a chair, walking a short distance, sitting on a chair), and thus represent tests that are more likely to be safely performed in a (future) unsupervised setting. Nevertheless, there are some potential risks associated with these performance tests being conducted outside of the clinic setting.

Protection against risks during the physical performance tests will include the following:

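### Section 8.1.b bases the validity limit on Phase 1 timing by two direct observers, but sections 9.0 and 13.0 describe one investigator on video and one in the room

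*Combined protocol and SAP*

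**What the plan says.** Section 8.1.b calls videoconferencing valid if the limits of agreement lie within a clinically acceptable limit. The investigator and mentors are to set that limit "after the proof-of-concept portion of the study (first 10 participants". The reason given for waiting is that this phase will show how far raters differ "under ideal conditions (both investigators directly observing the tests at the same time". The limit is then to be "a limit that is at or above the inter-rater difference under ideal conditions". No value is given for the Timed Up & Go (TUG) or the 30-second chair stand test (30s-CST).

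Section 9.0 (Study Design) describes the same phase. Of the first investigator it says: "While one investigator is in a different room of the house conducting the videoconference assessment". The second investigator is placed with the participant and given a different task: "another will be in the same room to directly observe and evaluate the impediments and barriers related to the technology and test protocol". Section 13.0, on the home visits of Phases 1 and 2, describes one in-room team member: "This research team member will be timing the participant as part of the face-to-face assessment to be compared with remote (videoconferencing) assessment". Section 2.0 also has one person in the room for the validity comparison: "a member of the research team will need to be at the participant's home, and in the same room as the participant". Section 8.2 is looser: "one or more members of the study team will be present in the home during the performance tests".

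The Analyses part of section 10.0 repeats the limits-of-agreement rule but mentions neither Phase 1 nor the floor. Hypothesis 1.1.c attaches the phrase about a clinically acceptable limit to a different quantity, an ICC of at least .80.

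**The concern.** The limits-of-agreement rule decides whether the method is called valid, and the Phase 1 rater difference is the only empirical anchor the protocol gives for its limit. If both investigators are to observe directly, neither can be the one on video in another room. Under the procedures as written, the benchmark is therefore not collected.

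What Phase 1 does supply, taking section 13.0 as correct that the in-room member times the tests, is a live video-versus-in-person difference. That difference contains the video error under test. A team looking for the rater difference that section 8.1.b promises could take this one, since it is the only live pair available. The worse the video method performed in Phase 1, the wider the limit for Phase 2 would then become.

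**Working it through.** **Comparing the sections.** There is no figure in the plan to reproduce; the point rests first on the text.

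| Section | Phase 1 arrangement |
|---|---|
| 8.1.b | both investigators observe directly and simultaneously |
| 9.0, Study Design | one on video in another room; one in the room, assigned to look at barriers (timing not mentioned) |
| 13.0 | one in-room member, who times, for comparison with the remote assessment |
| 8.2 | one or more team members in the home |

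Section 8.2 permits a second in-room timer but does not schedule one. In Phase 1 the video assessor is already in the house, which could account for the plural. The three or more additional scorers in section 9.0 work from recordings, so they do not observe directly. Nor can direct observation be read as watching live by video, because the Phase 2 description in section 1.0 equates it with face-to-face assessment.

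**Why the two differences are not interchangeable.** Let each rater have timing variance s_r², and let video add variance s_v² (neither is given). For independent raters:

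- direct versus direct: variance of the difference = 2s_r²
- video versus direct: variance of the difference = 2s_r² + s_v², plus any systematic video delay as bias.

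The second is the quantity that Phase 2 evaluates.

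**Size, as an illustration only.** Sample sizes come from section 1.0: 10 or 12 in Phase 1 and 10 or 20 in Phase 2. Everything else is assumed: normal TUG differences, zero bias, equal SD in both phases, and a 1 s clinical limit. The rule simulated is: pass if |mean₂| + 1.96·SD₂ ≤ max(1 s, floor), with 200,000 pairs of samples per setting. The floor is either absent (fixed limit), the Phase 1 video-versus-in-person limits of agreement |mean₁| + 1.96·SD₁, or a Phase 1 mean difference (absolute mean, or mean absolute difference).

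| Difference SD | True half-width, 1.96 × SD | Pass, limits-of-agreement floor | Pass, fixed 1 s |
|---|---|---|---|
| 0.35 s | 0.69 s | 0.92-0.98 | 0.91-0.98 |
| 0.4 s | 0.78 s | 0.78-0.89 | 0.76-0.87 |
| 0.5 s | 0.98 s | 0.57-0.62 | 0.38-0.39 |
| 1 s | 1.96 s | 0.49-0.52 | under 0.005 |

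- With either mean-difference floor, the pass probability at SD 1 s is at most 0.006, so the effect is negligible.
- With a floor from genuine direct-versus-direct timing (assumed SD 0.1-0.3 s), it is at most 0.005, the same as with the fixed limit. The problem is the source of the floor and not the idea of having one.
- At SD 1 s the median limits-of-agreement floor is 2.1 s, which the mentors could reject as not clinically acceptable.
- If the Phase 2 SD is 1.5 times the Phase 1 SD of 1 s, the pass probability falls to 0.07-0.11.

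**The case against.** The strongest reply is that the plan may be incomplete and not wrong. Section 8.1.b itself says that two investigators observe directly, and section 9.0 does not say that every Phase 1 test is run only in the video arrangement. A two-observer timing component may simply be missing from section 9.0. This stands: the documents do not show which section is in error, and the fix must allow for either.

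A second reply is that the harm is hypothetical. That also stands in part. A reader might infer that the limit will be built from the video-versus-in-person difference and that the validity test is therefore circular. The documents do not support this. No section says that difference will be used, the statistic is not named, and the rater difference is only a floor under a limit that must still be clinically acceptable. The roughly 50% pass rate follows almost automatically from comparing two samples with equal SD under a mechanical rule, and the contrast with the fixed limit is much smaller for a borderline method.

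A reader might also infer, because Phase 2 was under way when this version was written, that Phase 2 differences were seen before the limit was set. No section suggests this; section 8.1.b places the decision before Phase 2.

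Finally, this is a small pilot, and section 3.0 names feasibility, acceptability and safety as its primary aims. Section 1.0, however, makes validity and reliability the primary objective, so the rule deserves a sound basis.

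**Conclusion.** The inconsistency holds on the text alone, with no assumptions. Section 8.1.b relies on a Phase 1 benchmark that sections 9.0 and 13.0, as written, do not measure. The investigator and mentors can still set a limit by judgment, so the validity rule remains usable, but its stated empirical basis is missing.

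The consequence for the validity decision is conditional. It is material only if the video-versus-in-person difference is applied mechanically as a limits-of-agreement floor: about 50% against under 0.5% at an assumed SD of 1 s, and about 57-62% against 38-39% at 0.5 s, with an assumed 1 s limit. With a mean-difference floor it is negligible. The documents give no SD and no limit, so these figures show the mechanism and do not predict this study's result. The point should be fixed; it does not show that the validity result will be biased.

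**What to change.** 1. Reconcile sections 8.1.b, 9.0 and 13.0. Either describe in section 9.0 the timing by two direct observers, if it was or will be done, or correct section 8.1.b to say what Phase 1 actually estimates.
2. State in section 8.1.b and in the Analyses part of section 10.0 that the limit will not be derived from any video-versus-in-person difference.
3. If a rater-difference floor is kept, take it from direct-versus-direct timing and name the statistic. Otherwise drop it and set the limits for TUG (seconds) and 30s-CST (stands) on clinical grounds, documented before Phase 2 differences are examined. The COVID-19 modifications in section 9.0 say home visits were not allowed at restart, so if no direct-versus-direct timing was collected earlier, the clinical limits would have to stand alone.
4. Align hypothesis 1.1.c with the limits-of-agreement rule. An ICC of at least .80 is not a limit in seconds or stands.
5. Because Phase 2 had begun by this version, record when the limit was fixed.

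The cost is wording changes and one documented decision. No extra visits, raters or participants are needed unless the team keeps the floor without having direct-versus-direct data. The downside is that the study may fail a limit it would otherwise have passed.

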### 8.2 Primary and secondary safety endpoints

All adverse events associated with the performance tests (see section 9.0) will be tracked. The performance tests incorporate movements typically undertaken during normal daily activities (standing from a chair, walking a short distance, sitting on a chair), and thus represent tests that are more likely to be safely performed in the home. For both the proof-of-concept and validation studies, one or more members of the study team will be present in the home during the performance tests. Safety checks will be made prior to the performance tests (see section 13.0 Potential Risks to Subjects / Protection Against Risks).

## 9.0 Procedures Involved

### *Study Design*

Interested and eligible participants will be scheduled for a home visit (Phases 1 and 2). An android tablet with Wi-Fi and cellular will be used to compare videoconferencing with face-to-face assessment of 2 timed, physical performance tests. The tablet will contain videos demonstrating the performance tests, safety measures, and instructions, with features adapted for older adults (e.g., large font).\*\* Further instructions will be provided by the investigator via videoconferencing. First, we will test proof-of-concept that participants will be able to follow the testing protocol and use the tablet to communicate with the investigator (10-12 participants). While one investigator is in a different room of the house conducting the videoconference assessment, another will be in the same room to directly observe and evaluate the impediments and barriers related to the technology and test protocol. After refining the study protocol and materials, 10-20 participants will be enrolled to evaluate the validity and reliability of videoconference vs. face-to-face assessment of physical performance. The performance tests will be assessed simultaneously by two investigators to eliminate intra-participant variation that would occur with sequential assessments. A simultaneous assessment (face-to-face and remote) vs. sequential assessments avoids learning effects (among high performers) and fatigability (among low performers). One investigator will perform the assessment from a remote location using videoconferencing (provides

